7.1.2 Study Scheme Diagram

7.2 Study Populations

7.2.1 Intention- to-treat population.

Results will be presented on an intention to treat basis with all randomised patients analysed according to the group they were assigned to, regardless of whether the treatment was received or whether the protocol was adhered to.

7.2.2 Safety population

The safety population will consist of all randomised patients who received the allocated treatment.

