9.3 Procedure protocol

9.3.1 All patients

Patient gives informed consent in pre-admission. Patients will be blinded to their ECG and rhythm. Admitted to day ward. Arrival in Lab and checked in as for Cryo PVI. Skin electrodes placed. Conscious sedation or GA administered and sterile field prepared. 8F and 7F sheaths placed in RFV under ultrasound guidance. Heparin given as per local AF ablation protocol.

Once sheaths in place and GCS < 10, randomisation will be performed via REDCap, a web-based, electronic database. Patients will be randomised in a 1:1 ratio to either DCCV+ PVI or DCCV alone.

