9.10 Subject Withdrawal

Patients can withdraw from the trial at any time and without giving a reason. The Principal Investigator can also withdraw a patient from the study for any of the following reasons:

1. Any adverse event or serious adverse event
2. Any concurrent illness that prevents further treatment
3. Any change in the patient's condition that justifies the discontinuation of treatment in the clinician's opinion
4. Withdrawal of consent for treatment by the patient
5. Any study device or procedural complications
6. Any reasons the subject cannot adhere to study visits or procedures

If a patient withdraws from the study, another patient will be randomised to replace them. Patients who are randomised but withdraw will not have their medical care affected and return to standard clinical care.

10. Assessment and management of risk

The risks of both DC cardioversion and of catheter ablation for AF are well established, as detailed below. However, the procedures will be performed by experienced clinicians who part of the research team for all study participants, which should minimise any known/expected risks.

10.1.1 DCCV risks:

- Sedation complications (<1%), chest discomfort, redness, irritation at site of skin pads (5%), failure of DCCV.

10.1.2 Catheter ablation of AF risks:

- Groin access complications (1% historically, <0.2% with ultrasound guidance)
- Minor (Total <6%)
 - Groin: Bleeding bruising at groin access site (5%)
 - Pericardial effusion not requiring drainage (1%)
 - Transient phrenic nerve palsy (3%)
- Major (Total <1%)
 - Groin complication or vascular damage requiring surgical or radiological intervention (0.5%)
 - Cardiac tamponade requiring percutaneous drainage (0.7%)
 - Stroke (<0.2%)
 - Oesophageal damage (<0.2%)
 - Death (<0.1%)
 - Pulmonary vein stenosis causing breathlessness (<0.1%)

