17.3 Notification and reporting of Adverse Events and Reactions

If the AE is not defined as serious, the AE will be recorded in the study documents and the participant followed up by the research team. The AE will be documented in the participants' source documents, the Case Report Form (CRF), and, where appropriate, medical records.

The following events will be considered and reported as Adverse Events, and not serious adverse events, as they are expected as known complications of procedures:

- Phrenic nerve damage
- Tamponade or pericardial effusion
- Haematoma
- Skin Burns
- Chest pain
- Groin vascular complications.

The period for adverse events reporting will be from the signing of consent until the end of study visit at 12 month follow-up.

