17.4 Serious Adverse Events (SAEs) or reactions

A serious adverse event (SAE) is defined as an untoward occurrence that:

- Results in death,
- Is life-threatening,
- Requires hospitalisation or prolongation of existing hospitalisation,
- Results in persistent or significant disability or incapacity,
- Consists of a congenital anomaly or birth defect, or
- Is otherwise considered medically significant by the investigator.

SARs will be reported to the REC where in the opinion of the Chief Investigator the event was serious and:

- Related (it may have resulted from administration of any of the research interventions), and
- Unexpected (the type of event is not listed in the protocol or other Reference Safety Information as an expected occurrence).

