6.4.4 Assessment of feasibility endpoints

Protocol non-adherence is defined as the proportion of patients in each randomised group who undergo the treatment that they were not randomised to as part of the index procedure, i.e. those randomised to DCCV only undergoing DCCV plus PVI, and those randomised to the DCCV plus PVI group who only undergo DCCV as part of the index trial procedure.

Recruitment rate will be defined as the total number of patients recruited divided by the number of months during which recruitment takes place.

Loss to follow-up will be defined as a) the number lost to follow-up at 12 months as a proportion of the number randomised. b) the number who do not consent to the collection of 5-year registry data as a proportion of the number randomised.

Data completeness will be defined as the number of subjects completing each assessment as a proportion of the total randomised. For this pilot study, analyses will be conducted on a complete case basis, and the level of missing data will be assessed to help inform as to best methods to use to handle potential missing data within a larger future trial.

Blinding index will be assessed as described by Bang et al (BI)². Patients and staff will be asked to guess the treatment allocation and will answer DCCV, DCCV+PCI, or don't know. The BI is scaled to an interval of -1 to 1 with 1 being complete lack of blinding, 0 being perfect blinding and -1 indicating opposite guessing.

Other feasibility endpoints including assessing study logistics, identifying barriers and facilitators to implementation, and assessing the acceptability of the interventions will be assessed qualitatively, and hence will not be described further in the SAP.

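### The safety population leaves out patients who did not receive their allocated treatment, and Protocol 17.3 makes tamponade and groin vascular complications non-serious because they are expected, contradicting 17.4

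*SAP*

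**What the plan says.** **Safety population.** SAP 7.2.2 reads: "The safety population will consist of all randomised patients who received the allocated treatment". The title of Table 5 (adverse events) names this population. No rule assigns patients to the procedure they actually had, and receipt is not defined for a partly completed ablation.

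**Timing of exposure.** Protocol 9.3.1: "Once sheaths in place and GCS < 10, randomisation will be performed via REDCap". Sedation and venous access therefore come before allocation in both arms.

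**Non-receipt is foreseen.** SAP 6.4.4 counts as non-adherence both the DCCV patients who have PVI at the index procedure and "those randomised to the DCCV plus PVI group who only undergo DCCV as part of the index trial procedure". Table 2 reports the proportions.

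**Seriousness.** Protocol 17.3 lists phrenic nerve damage, tamponade or pericardial effusion, haematoma, skin burns, chest pain and groin vascular complications. It says they "will be considered and reported as Adverse Events, and not serious adverse events, as they are expected as known complications of procedures". Protocol 17.4 defines an SAE by outcome, for example "Requires hospitalisation or prolongation of existing hospitalisation", with no exception for expected events. Expectedness enters 17.4 only as a further condition for reporting to the REC: an event is unexpected if "the type of event is not listed in the protocol or other Reference Safety Information as an expected occurrence".

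**Major risks.** Protocol 10.1.2 places tamponade needing drainage (0.7%) and groin or vascular damage needing intervention (0.5%) among the major risks of ablation.

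**The concern.** Comparing the safety of the two strategies is a stated objective (Protocol 6.2). A safety population that depends on receiving the allocation can lose a patient because of the very harm being measured: a complication stops the ablation, the allocation is not received, and the event leaves the table.

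The 17.3 rule acts on a different output. Table 6 is the only planned output that lists individual events by term, and it holds SAEs only. A tamponade that meets a 17.4 criterion but is classed as non-serious would not appear there. Nor would it follow the Protocol 17.8 route by which SAEs go to the trials unit.

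The two rules compound. A tamponade that ended a PVI could be missing from both Table 5 and Table 6, leaving it in the planned tables only as an unnamed count in Table 4.

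The direction of bias is not uniform. It favours PVI most clearly for tamponade and abandoned ablation. Groin events can occur in both arms (Protocol 10.1.3), and dropping an ablated DCCV patient does not by itself favour PVI.

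**Working it through.** The plan gives no figure to reproduce here. The check is a comparison of the rules, followed by arithmetic to show scale.

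**Step 1: who leaves Table 5.**

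| Patient | Exposed to the procedure? | In the ITT population (SAP 7.2.1)? | In the safety population (SAP 7.2.2, literal)? |
|---|---|---|---|
| PVI arm, completed | yes | yes | yes |
| PVI arm, abandoned, DCCV only | yes | yes | no |
| PVI arm, partly completed | yes | yes | undefined |
| DCCV arm, given PVI at index | yes | yes | no |

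**Step 2: effect of one case.** Inputs: 10 per arm, one abandoned PVI with a complication and no other events.
- All randomised: 1/10 = 10% (exact 95% CI 0.3% to 44.5%).
- SAP 7.2.2: 0/9 = 0% (exact 95% CI 0% to 33.6%).
- Table 4 (ITT) would still show 1/10 for related complications.

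The documents give no abandonment rate. If it were 5% to 10% (assumption), the chance that at least one of 10 PVI patients drops out of Table 5 is 1 − 0.95^10 = 40% to 1 − 0.90^10 = 65%. That counts any abandoned case, with or without a complication.

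**Step 3: 17.3 against 17.4.** Under 17.4, seriousness is decided by outcome, and expectedness is then applied to decide REC reporting. Under 17.3, expectedness decides seriousness, with no limit on severity. SAP 12.2 and Table 6 record for each SAE whether it was expected, which makes sense only if an expected event can be serious. Protocol 17.5 already confines expedited reporting to related and unexpected SAEs, so 17.3 is not needed for that purpose.

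**Step 4: how often 17.3 would matter.** Inputs: the two major items in 10.1.2 that 17.3 also lists, assumed additive: 0.7% + 0.5% = 1.2%. Formulas: expected events = n × p; chance of at least one = 1 − (1 − p)^n.

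| Rate p | n = 10: expected, chance | n = 104: expected, chance |
|---|---|---|
| Tamponade and groin/vascular, 1.2% | 0.12, 11.4% | 1.25, 71.5% |
| Tamponade only, 0.7% | 0.07, 6.8% | 0.73, 51.8% |

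Stroke, oesophageal damage, death and pulmonary vein stenosis are left out because 17.3 does not list them.

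**Step 5: totals in 10.1.2 (editorial).** Two major items already sum to 1.2%, against a stated total below 1%. The minor items sum to 5% + 1% + 3% = 9% (1 − 0.95 × 0.99 × 0.97 = 8.8% with at least one, if independent), against a stated total below 6%. Only substantial overlap of events in the same patients would reconcile these figures.

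**The case against.** **Receipt may be read more generously.** SAP 6.4.4 speaks of PVI-arm patients who had DCCV only, and a patient with a transseptal puncture and some freezes has had more than that. This stands for a partly completed PVI, whose status is undefined rather than clearly excluded. It does not help a patient whose procedure stopped before any freeze. The parallel argument, that a DCCV patient given PVI still received the allocated DCCV, is weak, since 6.4.4 describes that patient as having had the treatment not assigned.

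**The event survives elsewhere.** This largely stands. Table 4 (ITT) has rows for related complications, bleeding within 7 days and hospital admission. Table 6 and the text of SAP 12.1 and 12.2 name no population. Non-serious AEs go into the CRF, the CI reviews reported events, and the DSMC sees unblinded data. Expected events would not be expedited to the REC in any case. These offsets limit the damage but leave the safety table and the SAE listing wrong.

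**The 17.3 list might mean mild forms only.** It follows a sentence about AEs not defined as serious. But the reason it gives is expectedness, and it names tamponade without qualification.

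**The groin rate may be too high.** Protocol 10.1.2 also gives groin access complications below 0.2% with ultrasound guidance, which every patient has. With that bound, the sum is at most 0.7% + 0.2% = 0.9%: 0.09 events in 10 patients (8.6% chance of at least one) and 0.94 in 104 (61%). This is a fair lower variant. It changes the illustration and not the contradiction.

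**The main-trial figures are conditional.** They are: expansion depends on funding, pilot results and an ethics amendment. SAP 6.1 does, however, carry pilot patients into the main trial if the design has no major change.

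**Conclusion.** Both main points hold and should be fixed. As written, SAP 7.2.2 can remove exposed patients from the adverse event table, including patients whose harm caused the non-receipt. Protocol 17.3 contradicts 17.4, sits badly with the major class in 10.1.2, and defeats the expected/unexpected column of Table 6. No other section repairs this.

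The practical size in the pilot is modest. The population rule bites only if a case occurs, and one case moves Table 5 from 1/10 to 0/9. The seriousness rule would affect at least one major event with a probability of about 9% to 11% in 10 ablated patients. If the definitions carry into a main trial of 104 per arm, that becomes about 61% to 71.5%. These ranges rest on the protocol's own rates, assumed additive, with the groin item at 0.2% or 0.5%. The mismatch in the 10.1.2 totals is a side note and does not affect the conclusion.

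**What to change.** 1. **SAP 7.2.2 and Table 5.** Define the safety population as all randomised patients, tabulated by the procedure actually received. Show any transseptal puncture or attempted PVI with PVI. Table 4 already gives the as-randomised view.
2. **Protocol 17.3 and 17.4.** Reconcile them so that a listed event meeting a 17.4 criterion is recorded as an SAE and appears in Table 6 as expected. The 17.3 list should then govern expedited reporting only.
3. **Protocol 10.1.2 (editorial).** Reconcile the major and minor totals with their components.

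The cost is wording in one SAP section and one protocol section, the editorial correction, and a few more SAE forms. No procedures or visits are added.

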7.3 Subgroup definitions

No subgroup analysis will be undertaken.

7.4 Treatment assignment and treatment groups

Patients will be randomised on a 1:1 basis to either DCCV alone or DCCV + PVI. Block randomisation is used with randomly varying block sizes of length 2, 4, and 6. Randomisation will not be stratified by any factors. The allocation algorithm is written by the study statistician using R (randomizeR package). Details of the randomisation method and validation details are stored in a separate document which can be accessed by the trial statistician and the database manager.

The randomisation list will then be uploaded to the study database (REDCap). When a patient has been screened and has met all of the entry criteria in order to be eligible for trial participation, the unblinded investigator will go to the randomisation module on the database and complete the randomisation form. Once complete, the allocation (which is next in the sequence on the randomisation list) will be revealed to the unblinded investigator.

8 Patient Disposition

Participants will be those referred for either cardioversion for persistent AF (> 7 days) or catheter ablation of persistent AF. Inclusion/exclusion criteria are detailed in the protocol (section 7). Numbers of patients screened, excluded prior to randomisation by reason and overall, randomised and completing each phase of the study will be shown by treatment groups and overall following the Consort structure.

9 Demographics and Baseline characteristics

Demographic and baseline (screening data) will be:

1. Age
2. Sex
3. Ethnicity

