	
months to set up, 3 months to recruit, treatment (1 day), 3 month follow up and 2 months study closure. For the larger trial in 4-5 UK centres: Set-up 6 months, 6 month recruitment, treatment (1 day), 12 month follow-up, 3 months study closure.

--	---

5. Introduction

Patients with persistent atrial fibrillation undergoing catheter ablation are reported to have fewer symptoms and better quality of life than those undergoing DC cardioversion (DCCV) or optimal medical therapy. However, as yet this has not been subjected to a randomised, prospective, blinded clinical trial (January et al., 2014).

Atrial fibrillation (AF) is the commonest cardiac arrhythmia, with a prevalence of 5.5% (Heeringa et al., 2006). A major cause of the life-changing complication of stroke, AF is associated with severe symptoms, such as palpitations, shortness of breath, lethargy and a reduced quality of life. AF can be classified into paroxysmal, persistent or long-standing persistent. Paroxysmal AF refers to when episodes last less than 7 days before spontaneously termination, persistent AF implies episodes lasting greater than 7 days or requiring either electrical or pharmacological cardioversion, and longstanding persistent AF describes AF episodes lasting more than one year in duration trial (January et al., 2014).

Patients differ widely in the diversity and severity of their AF symptoms. Some 15-30% of patients with AF are asymptomatic. Data from implantable cardioverter-defibrillators (ICDs) and pacemakers have demonstrated that up to 70% of paroxysms of AF are asymptomatic. There is a need to clarify the relationship between patient reported symptoms and the arrhythmia itself. It is likely that both somatic and psychological factors contribute to this relationship. Patient perception or awareness of symptoms is often not a good discriminator of the severity of the arrhythmia. In the present study we will also collect information from patients on reported symptoms and effects on quality of life (both physical and mental), functional status and treatment satisfaction. We will be able to look at these and assess the correlations between reported symptoms and arrhythmia as captured by the LINQ device.

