5.3 Clinical data

Catheter ablation of AF is less established in patients with persistent AF, but compelling evidence exists that AF recurrence is reduced in patients with persistent AF who undergo catheter ablation when compared to electrical cardioversion plus antiarrhythmic medication. The SARA study (Mont et al., 2014) randomised 146 patients with persistent AF to antiarrhythmic medication plus electrical cardioversion or to catheter ablation, with 60% vs 30% of patients having recurrence of their arrhythmia at one year. The recent STAR-AFII trial (Conti et al., 2017) confirmed pulmonary vein isolation as the cornerstone of catheter ablation in this patient group, with no difference in the recurrence rates of patients undergoing AF ablation with pulmonary vein isolation alone (41% recurrence) or those who had pulmonary vein isolation plus electrogram ablation (51%) or plus linear ablation (54%) (Verma et al., 2015). Similar or greater rates of freedom from AF after a single procedure have been seen in registry data, with up to around 80% long-term freedom from AF with multiple procedures (Hunter & Schilling, 2010; January et al., 2014).

These data imply that the newer one-shot technologies such as the cryoballoon which provide durable PVI from a single, rapid, safe procedure, and thus would be effective in the ablation of persistent atrial fibrillation. Registry data support this assumption, with between 55 and 70% of persistent AF patients maintaining long-term sinus rhythm following cryoablation PVI (Ciccone et al., 2015; Coutino et al., 2016). These assumptions are being tested in ongoing clinical trials, where the efficacy of cryoablation PVI is being tested against point-by-point radiofrequency ablation.

However, it is well established that the effectiveness of any therapy aiming for rhythm control is determined in part to the duration of AF (Kirchhof & Calkins, 2017; Voskoboinik et al., 2017). The mantra “AF begats AF” has repeatedly been shown to be relevant to catheter ablation of persistent AF (Wijffels, Kirchhof, Dorland, & Allessie, 1995). The enthusiasm for treating AF aggressively early in the course of

the disease is reflected in recent NICE guidelines (Jones et al., 2014). A treatment strategy where patients have a definitive PVI procedure early may be far more effective, and prevent multiple repeated hospital attendances. Side-effects of antiarrhythmic medications may be also be avoided.

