7.1 Inclusion criteria

Patients who meet the following inclusion criteria will be eligible for the study;

- Ability to give informed consent
- Age 18-80 years
- Persistent AF (atrial fibrillation lasting > 7days) of total continuous duration <2 years as documented in medical notes.
- Patients being considered for cardioversion.

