11.1 Sample size

The sample size of 20 subjects for the pilot study has been chosen as an achievable recruitment target that would enable assessment of feasibility of the study, and to confirm whether a larger trial could be conducted.

The sample size for the larger trial is calculated based on the comparison of recurrence free survival in the two groups using the logrank test. The expected percentage of patients with recurrence of AF within one year is 47% for the ablation group¹ and 66% for DCCV^{2,3,4} based on published data. This is equivalent to a hazard ratio of 1.7. To detect an effect of this size with 80% power at the 5% significance level would require N=104 patients in each group.

For secondary endpoints the sample size of 104 patients will give 80% power at the 5% significance level to detect an effect size of 0.4 standard deviations in any continuous variable.

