6.5 Level of significance

No hypothesis testing will be done for this pilot study.

For efficacy outcome measures we will use 80% one-sided confidence intervals to give an indication of whether the endpoint is likely to be of interest, an approach described by Cocks et al. for pilot trials⁴.

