11.1.4 Covariate adjusted analysis

No covariate adjustment will take place.

11.2 Assumptions for analysis.

For continuous efficacy outcomes, confidence intervals for differences will be constructed assuming a normal distribution. Normality of distribution for continuous variables is hard to assess with such a small number of subjects in this pilot trial and so will not have much value.

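### The main-trial log-rank test is not specified as stratified by AF duration, a baseline factor the protocol calls a partial determinant of success: a forgone gain in power, not a shortfall

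*SAP*

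**What the plan says.** Protocol 5.3 accepts AF duration as prognostic: "it is well established that the effectiveness of any therapy aiming for rhythm control is determined in part to the duration of AF". The entry criterion in Protocol 7.1 is "Persistent AF (atrial fibrillation lasting > 7days) of total continuous duration <2 years as documented in medical notes". That range crosses a line drawn in the protocol's own Introduction, where "longstanding persistent AF describes AF episodes lasting more than one year in duration". Estimated AF duration is among the screening items in the schedule of assessments (Protocol 9.4), so it is known before randomisation.

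The SAP lists AF duration among the baseline characteristics (Section 9) and shows it by arm in Table 1 (Section 13). It has no other use. SAP 7.4 says "Randomisation will not be stratified by any factors" and SAP 11.1.4 says "No covariate adjustment will take place". This SAP covers the 20-patient pilot only, for which "No hypothesis testing will be done for this pilot study" (Section 6.5).

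For the main trial, Protocol 4 and 11.1 base the sample size on the "comparison of recurrence free survival in the two groups using the logrank test". Neither place says whether the test is stratified. Protocol 11.2 leaves analysis methods to a SAP, and the documents contain no SAP for the main trial.

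**The concern.** When a baseline factor predicts the outcome, a log-rank test that compares like with like within levels of that factor is usually more powerful than one that pools everybody. Here the protocol itself identifies such a factor, supplies a natural cut-point, and collects the value before allocation. A main trial of 208 patients with implanted recorders and a sham-type control is expensive, and any power available from existing data is worth taking.

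The choice also needs to be made in advance. If the primary test is described only as a log-rank test, both a stratified and an unstratified analysis fit the description, and they can give different p-values. Fixing it in the protocol before main-trial data exist removes that freedom.

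**Working it through.** **Inputs from the documents** (Protocol 11.1): 1-year recurrence 47% with ablation and 66% with DCCV; hazard ratio 1.7; 80% power; 5% significance; 104 per group. Sidedness is not stated; two-sided is assumed and reproduces the figure.

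**Reproducing the plan's figure.**
- Hazard ratio: ln(1 - 0.66) / ln(1 - 0.47) = 1.699, which rounds to 1.7.
- Events by Freedman's formula: (1.960 + 0.842)² × [(1.7 + 1)/(1.7 - 1)]² = 7.85 × 14.88, which rounds up to 117.
- Average event probability: (0.47 + 0.66)/2 = 0.565.
- Patients per group: 117 / 0.565 / 2 = 103.5, so 104. The figure reproduces.
- Schoenfeld's formula gives 112 events and 99.1, so 100 per group; Freedman's is evidently the one used.

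No stratum enters this calculation. The 80% is therefore the power of an ordinary log-rank test.

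**What stratifying would add.** The documents give neither the share of patients with AF over 12 months nor its effect on recurrence. Both are assumed: a share of 30, 40 or 50%, and a recurrence hazard ratio (over v up to 12 months) of 1, 1.5, 2 or 3. Each setting was simulated 6,000 times with exponential hazards, 104 per arm, 12 months of follow-up, and overall rates held at 47% and 66%. Allocation was not stratified. Power is in per cent.

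| Share over 12 months | Duration hazard ratio | Ordinary test | Stratified test | Difference (points) |
|---|---|---|---|---|
| 30% | 1 | 81.6 | 81.4 | -0.2 |
| 30% | 1.5 | 82.3 | 82.9 | 0.6 |
| 30% | 2 | 83.3 | 85.5 | 2.2 |
| 30% | 3 | 82.9 | 89.8 | 6.9 |
| 40% | 1 | 82.8 | 82.4 | -0.4 |
| 40% | 1.5 | 81.5 | 82.3 | 0.8 |
| 40% | 2 | 82.6 | 85.2 | 2.6 |
| 40% | 3 | 82.5 | 90.1 | 7.6 |
| 50% | 1 | 81.7 | 81.4 | -0.3 |
| 50% | 1.5 | 81.0 | 82.0 | 1.0 |
| 50% | 2 | 82.1 | 85.0 | 2.9 |
| 50% | 3 | 83.2 | 89.9 | 6.7 |

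The Monte Carlo error of each power is about 0.5 point: √(0.82 × 0.18 / 6,000) = 0.005. Across repeat simulations under the same assumptions the gain was 2 to 4 points at a duration hazard ratio of 2 and 7 to 9 points at 3. The table lies towards the lower end of the second range, and a larger repeat also came out near 7, so 7 is the safer reading.

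The gain arises because the treatment hazard ratio within strata is larger than the pooled 1.70: about 1.74-1.75 when duration doubles the hazard and about 1.82-1.83 when it triples it.

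**Is the ordinary test valid?** With no treatment effect it rejected in 5.4-5.5% of runs (Monte Carlo error about 0.3 point), in line with 5%.

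**Does the randomisation list need to change?** Adding stratified allocation to the stratified test gave 85.1-85.5% at a hazard ratio of 2 and 89.7-90.3% at 3 (shares of 30% and 50%), against 85.0-85.5% and 89.8-89.9% from the stratified test alone. Nearly all of the gain comes from the test. By exact hypergeometric calculation for an equal split, a between-arm gap of 20 points or more in AF over 12 months has probability 0.1-0.3% at 208 patients, but 63-66% at 20.

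**The case against.** The strongest reply is that nothing here is an error. The documents do not call the main log-rank test unstratified; they are silent, and the main trial still needs funding and an ethics amendment (Protocol 6.1). The ordinary test holds its level and exceeded 80% power in every setting above. The larger gains rest on a hazard ratio that no document supplies; at 1.5 the gain is about 1 point or less. All of this stands, and it is why the point is a modest improvement.

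A reader might infer that the pilot is harmed and that its list should be stratified or its estimates adjusted. The documents do not support that. The pilot tests no hypothesis, so it has no power to lose, and none of the progression criteria in Protocol 11.2 is a treatment-effect threshold.

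Imbalance is likely with 10 per arm, but its effect is small beside ordinary sampling error. Take 40% over 12 months and a tripled hazard. One-year recurrence then differs by about 37 points between long and short duration, so a 30-point imbalance (3 patients) moves the risk difference by 0.30 × 37 = 11 points. The standard error of that difference is √(0.47 × 0.53/10 + 0.66 × 0.34/10) = 0.22, or 22 points. If the pilot is pooled into the main trial, 3 of 104 is 2.9 points, which moves recurrence by about 1 point against a design difference of 19.

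Smaller blocks within strata would also make the next allocation easier to guess for the unblinded investigator who randomises (SAP 7.4).

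**Conclusion.** The point holds as a forgone gain. The protocol names a prognostic factor, enrols across its own cut-point, records the value before allocation, and does not say that the main-trial primary test will use it. Specifying stratification is worth about 0 points of power if duration is not prognostic, about 2 to 4 if AF over 12 months doubles the hazard, and about 7 to 9 (more safely, 7) if it triples it. The share of 30-50% and the hazard ratios are assumptions. Duration is an estimate taken from medical notes, and misclassification would shrink the gain.

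Two stronger readings should be resisted. The trial is not underpowered for want of stratification: 104 per group was derived without it and reproduces. Nor does the protocol say that AF duration governs the outcome; it says that duration determines success in part.

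**What to change.** In Protocol 4 and 11.1, state that the main-trial primary analysis is a log-rank test stratified by AF duration at screening (up to 12 v over 12 months, the protocol's own boundary), with a Cox hazard ratio stratified in the same way. Say that this hazard ratio is a within-stratum comparison, because it can differ slightly from the pooled 1.7. Leave the sample size at 104 per group. Pilot patients can enter this analysis if they are pooled, because their duration is recorded.

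Leave SAP 7.4 and 11.1.4 as they are. The pilot stays descriptive, with AF duration by arm in Table 1 so that any imbalance is visible.

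The cost is a sentence in each protocol section and a line of analysis code. The downside is a negligible loss of power if duration turns out not to be prognostic: 0.2 to 0.4 point in the table, which is within simulation error.
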